3.2. SECONDARY OUTCOMES

- (i) Oxygenation response at 24 h after initiation of study drug assigning a minimum OI of 40 or OSI of 20 (if no arterial blood gas is available) for subjects that need ECMO or die after initiation of study drug infusion but prior to 24h of study-drug infusion. In this analysis if the patient's OI is 30 (or OSI of 15) and is cannulated for ECMO due to hemodynamic instability, he/she will be assigned an OI of 40 (or OSI of 20). However, if the OI prior to ECMO is 47 (i.e., > 40), the higher number (47) will be used for analysis of this secondary outcome.
- (ii) Oxygenation index at 48 and 72 h after initiation of study drug (or OI/OSI at the time of initiation of ECMO or immediately prior to death, for infants placed on ECMO or died before these time points),
- (iii) Change in echocardiographic findings – velocity of tricuspid regurgitation, left ventricular ejection fraction, position of the interventricular septum and direction of shunt at the PDA and PFO level – prior to and 24-72h after starting the study

medication. This outcome will be available only for those infants who have a pre-study drug echocardiogram and a second echocardiogram between 24-72 h after initiation of study drug. These data will be extracted from echocardiograms performed for clinical indications.

- (iv) Vasoactive Inotrope score and systemic blood pressure
- (v) Area under the curve for inspired oxygen after initiation of the study drug over the first 72 hours of study-drug infusion (or prior to ECMO or death, whichever is earlier) (Note: inspired oxygen and ventilator data from 4 time points per day – every 6 hours will be recorded to calculate area under the curve),
- (vi) If subsequent to the study drug, any additional inotrope or pulmonary vasodilator is used (such as iNO), we will evaluate the oxygenation response to these agents. If inotropes or vasodilators were used prior to the initiation of study drug, similar values will be recorded. The OI (or OSI) and $\text{PaO}_2/\text{FiO}_2$ ratio prior to and after initiation of the inotrope / vasodilator are recorded (these data are recorded at 6 hour intervals; the date and time of initiation of individual inotropes and vasodilators is recorded). The change in OI (or OSI) and $\text{PaO}_2/\text{FiO}_2$ ratio in response to these agents is evaluated as a continuous variable and arbitrarily classified into responders, partial responders and non-responders similar to prior trials (1997, 1997).

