2. One complete blood count (CBC) with a platelet count of $> 80,000/\text{mm}^3$ on the most recent evaluation prior to enrollment is required for randomization. This CBC may be drawn after one or multiple platelet transfusions.
3. The use of therapies such as sedation, analgesia, paralysis, surfactant, high frequency ventilation, iNO, pressors, inhaled prostaglandins (including PGE₁ and prostacyclin) and steroids are permitted at the discretion of the clinical team (and/or based on written center guidelines – a copy of each center's guidelines, if available, will be collected prior to enrollment).
4. Infants with CDH as part of a congenital syndrome that does not cause cardiopulmonary or renal compromise (e.g., rib cage anomalies, renal dysplasia) can be included in the study. Infants with trisomy 21 and CDH without cyanotic heart disease or kidney disease affecting renal function may be included in this trial.

5. A baseline echocardiogram (if ordered for clinical indications) prior to initiation of study drug or within 6 hours of initiation of study-drug is preferred as a baseline study. However, consenting, randomization and preparation of study drug by the pharmacy may proceed without an echocardiogram. It is not necessary to wait for the “official” results of the echocardiogram to commence study drug (unless there is a high suspicion for cyanotic congenital heart disease).

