4.2.3. Randomization Procedures

The following information must be checked and/or confirmed prior to randomization. (a) chest X-ray to confirm the presence of unilateral CDH, (b) complete blood count – CBC to check platelet count and (c) a blood gas – arterial, venous or capillary to document a $\text{PCO}_2 \leq 80 \text{ mm Hg}$. These labs are routinely obtained to evaluate babies with suspected CDH in most institutions. Data from a baseline echocardiogram prior to initiation of study drug (if obtained for clinical purposes) is recorded but is not necessary for randomization (see 4.1.2 (5) above).

- (i) The diagnosis of CDH and the side of the defect must be confirmed with a chest X-ray.
- (ii) Adequate platelet count ($\geq 80,000/\text{mm}^3$) on the most recent CBC (after a platelet transfusion if necessary).
- (iii) Optional - An indwelling arterial line is placed (if not available oxygen saturation index or OSI is collected).
- (iv) Concurrent, ongoing therapy with a parenteral (IV/SQ) pulmonary vasodilator (milrinone, epoprostenol, treprostинil or sildenafil) is a contraindication to the study.
- (v) An arterial blood gas (preductal or postductal) with an oxygenation index of ≥ 10 (or OSI ≥ 5 in the absence of an arterial blood gas) and an arterial, venous or capillary blood gas with $\text{PCO}_2 \leq 80 \text{ mmHg}$ on the most recent blood gas (or pulse oximeter recording) should be recorded within 12 hours prior to randomization. An acute reversible mechanical factor such as endotracheal tube obstruction as a cause of elevated OI should be ruled out prior to randomization. If both preductal and postductal gases are available (this is rare), a preference is given to preductal – right radial or ulnar arterial draws, for calculation of OI. (Gien and Kinsella 2016) The same site (preductal or postductal) must be used at various time points for consistent comparison.
- (vi) Infants with CDH are eligible for enrollment if there are no exclusions and the most recent blood gas drawn within 12 hours prior to randomization has an OI ≥ 10 .
 - a. In patients without arterial access and/or an arterial blood gas, oxygen saturation index (OSI) can be calculated and if ≥ 5 , randomization can be performed.

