Subject specimens: Information about blood counts, imaging and blood gases will be obtained from blood draws conducted for the purpose of clinical care. No additional blood work will be performed for the purpose of research.

Echocardiography: Data from a maximum of 4 clinical echocardiograms will be recorded. No additional echocardiograms will be performed for the purpose of this study. To estimate the secondary outcome of improvement in cardiac function and pulmonary hypertension, data from at least two echocardiograms will be obtained if available – the first echocardiogram preferably prior to initiation of the study drug. If echocardiogram is not performed prior to study drug initiation, study drug may be initiated.

If clinical echocardiograms are obtained during the study drug infusion, data from the clinical echocardiogram closest to 24 hours after study drug infusion is used to calculate the secondary outcome of change in echocardiographic findings. If a third echocardiogram is obtained close to 72 hours after initiation of study drug, data from this study will be recorded. In addition, data from any other echocardiograms obtained for clinical purposes after completion of study drug will be recorded (maximum of 4 echocardiograms).

Cranial ultrasound: As mentioned previously, an initial cranial ultrasound is obtained prior to initiation of study drug or within 4 hours of commencement of the study drug. A second cranial ultrasound is obtained preferably within 24 hours (maximum within 96 hours) of completion of the study drug. Both these cranial ultrasounds are covered by the study budget. Additional head imaging may be performed based on clinical indications but are not covered by the study budget. If the patient has a screening ultrasound that demonstrates intracranial hemorrhage

(as outlined in the exclusion criteria) prior to starting the study-drug, the patient is not randomized. In this case, only one screening cranial ultrasound is covered by the study budget.

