5.4 STATISTICAL ANALYSIS PLAN

Baseline data will be collected prior to randomization including gestational age, side of the diaphragmatic hernia, birth weight, mode of delivery and arterial blood gas parameters (oxygenation index-OI) and/or pulse oximetry data (oxygen saturation index-OSI). Data from a baseline clinical echocardiogram is recorded (if performed prior to study drug initiation or within 2h of initiation of study drug). During the infusion of study drug, arterial blood gas parameters and hemodynamic data (blood pressure, heart rate and echocardiography results) will be recorded. After completing the study infusion, surgical details, and mortality information will be collected. Among survivors, respiratory and nutritional status at discharge and at 4, 8 and 12 months of age will be collected.

Data will be presented as mean \pm SD for normally distributed variables and as median and ranges (with percentiles) for non-normally distributed data. All analysis will be by intention-to-treat. Baseline characteristics will be compared between treatment groups using chi-square and Fisher's exact test for discrete variables and t-test and ANOVA for continuous variables. The primary outcome, difference from baseline OI at 24 h, will be compared between treatment groups using a general linear model adjusted for the stratification factor of HRF severity. Other continuous outcomes will be analyzed similarly. Models for longitudinal outcomes such as oxygenation and vasoactive inotrope scores (short-term) and nutritional and pulmonary outcomes at 12 months (long-term) will include the effect of time, the interaction between time and treatment, and random effects to account for the correlation between measures taken on the same individual over time. Categorical outcomes will be analyzed using analogous generalized linear models. Cox regression models (with adjustment for HRF severity) will be used to plot proportion of responders who survive without ECMO against survival time in hours. Analyses may adjust for clinical site if treatment assignments are severely imbalanced for some sites provided that it is computationally feasible to do so. The potential influence of baseline measures such as time of diagnosis – antenatal vs. postnatal, side of the defect, and gender on pulmonary and nutritional outcome will be explored through the use of additional models similar to those described above.

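### Secondary outcome (iii) drops infants who have a 24-72 h echocardiogram but no pre-drug one, so the echo part of aim 1 loses avoidable precision

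*Combined protocol and SAP*

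**What the plan says.** Section 3.2(iii), repeated in the synopsis, is a change in tricuspid regurgitation velocity, ejection fraction, septal position and shunt direction. It restricts the analysis set: "This outcome will be available only for those infants who have a pre-study drug echocardiogram and a second echocardiogram between 24-72 h".

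Neither echo is a study procedure. Section 3.2(iii) states: "These data will be extracted from echocardiograms performed for clinical indications". Section 4.2.5 (Echocardiography) adds: "No additional echocardiograms will be performed for the purpose of this study".

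No pre-drug echo is required at any step:
- Section 4.1.2, note 5: "consenting, randomization and preparation of study drug by the pharmacy may proceed without an echocardiogram".
- Section 4.2.3, on the baseline echo: it "is recorded but is not necessary for randomization".
- Section 4.2.5: "If echocardiogram is not performed prior to study drug initiation, study drug may be initiated".

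For the analysis, Section 5.4 compares the primary outcome as a difference from baseline in a general linear model adjusted for HRF severity, then says: "Other continuous outcomes will be analyzed similarly". The random-effects models in that section give oxygenation, inotrope score and 12-month outcomes as their examples; echo is not mentioned. No section says what happens to an infant who has only a follow-up echo.

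**The concern.** The plan makes the first echo optional and then makes it a condition for entering the analysis. In a randomised comparison a pre-treatment measurement is a covariate. The arms have the same expected pre-drug mean, so the expected arm difference in change equals the expected arm difference in the follow-up value. An infant with only a 24-72 h echo therefore carries information about the treatment effect, and the pairs-only rule discards it.

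Echo change is named in the primary hypothesis (Section 2.1) and forms the second half of specific aim 1 (Section 2.2). The trial plans 33 infants per arm and relies on whatever clinical echoes exist, so the set of pairs may be small. Tricuspid velocity is available only if a jet is present (Section 4.2.4), which reduces it further for that measure.

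**Working it through.** **The plan's own figure.** Section 5.1 gives power only for OI: 33 per arm, difference 4.6, SD 6.2, two-sided alpha 0.05, power 84%. The noncentral t calculation gives 84.3%, so it reproduces. Nothing comparable is stated for echo.

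**Inputs.** From Section 5.1: 33 per arm. Assumed, because the documents give none of them:
- m, infants per arm with a 24-72 h echo. Taken as 33, an upper bound; the percentages and ratios below do not depend on m.
- f, the share of those infants who also have a pre-drug echo: 0.5, 0.7, 0.9.
- ρ, the correlation between the two readings: 0.5, then 0.3 to 0.8.

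**Variance of the arm difference**, in units of the squared SD of a single reading:
- Change score, pairs only: (2/m) × 2(1−ρ)/f
- Baseline-adjusted, pairs only: (2/m) × (1−ρ²)/f
- All follow-up echoes, longitudinal model with a common pre-drug mean: (2/m) / [f/(1−ρ²) + (1−f)]
- Follow-up value alone, all infants: 2/m

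The second and third lines differ only in the infants recovered, so comparing them isolates the cost of the pairs-only rule.

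**Worked case**, m = 33, f = 0.5, ρ = 0.5:
- adjusted pairs: (2/33) × 0.75/0.5 = 0.0909, SE 0.302
- all follow-up echoes: (2/33) / (0.5/0.75 + 0.5) = (2/33)/1.1667 = 0.0519, SE 0.228
- reduction in variance: 1 − 0.0519/0.0909 = 43%

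**Results at ρ = 0.5** (SE in SD units):

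| f | Pairs per arm | Change score | Adjusted pairs | All follow-up | Variance cut v adjusted pairs | Variance cut v change score |
|---|---|---|---|---|---|---|
| 0.5 | 16.5 | 0.348 | 0.302 | 0.228 | 43% | 57% |
| 0.7 | 23.1 | 0.294 | 0.255 | 0.222 | 24% | 43% |
| 0.9 | 29.7 | 0.259 | 0.225 | 0.216 | 8% | 31% |

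**Sensitivity to ρ.** For ρ from 0.3 to 0.8, the SE of adjusted pairs divided by the SE using all follow-up echoes is 1.17-1.38 at f = 0.5, 1.07-1.18 at f = 0.7 and 1.02-1.05 at f = 0.9.

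**Missing-indicator version.** Ordinary least squares with a missing indicator does not weight the two groups by precision. Its variance is (2/m) × [f(1−ρ²) + (1−f)].
- At ρ = 0.5 the brackets are 0.875, 0.825 and 0.775, against 1.500, 1.071 and 0.833 for adjusted pairs. The cuts are 42, 23 and 7%.
- At f = 0.5, ρ = 0.7 the bracket is 0.755, against 1/(0.5/0.51 + 0.5) = 0.675 for the longitudinal model, about 12% larger.
- At f = 0.9, ρ = 0.8 it is 0.424, against 0.36/0.9 = 0.400 for adjusted pairs. Here the unweighted model is slightly worse than pairs.

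**The case against.** The strongest reply is that the outcome and aim 1 are both defined as change from baseline, so a baseline is needed to compute them, and that it earns its place. A reader might infer that the pre-drug requirement buys nothing. The arithmetic does not support that: at f = 0.9 and ρ = 0.7 the change score in about 30 pairs has SE 0.201, against 0.246 for the follow-up value alone in all 33. The loss exists only relative to a model that uses the baseline where it is present and still keeps the other infants.

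Two limits on size also stand. The synopsis and Section 4.1.2, note 5 express a preference for an early first echo, and the same teams order both echoes. The pre-drug share among infants with a follow-up echo could therefore be high, which puts the gain near the bottom of the range. The calculation also covers only the two continuous measures; septal position and shunt direction are categorical.

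Finally, it can fairly be said that the later echo is the more serious problem. It is clinically triggered after randomisation and may be missing because of death, ECMO or improvement, so its availability can differ by arm. Recovering follow-up-only infants does not cure that.

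**Conclusion.** The point holds as a loss of efficiency in one unpowered secondary outcome. Compared with baseline-adjusted pairs, the avoidable variance is up to about 43, 24 or 8% for pre-drug shares of 50, 70 or 90% at correlation 0.5. These are illustrations, since shares and correlation are assumed. If nearly every infant has a pre-drug echo, the loss is small.

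Three stronger readings are not supported:
- *That the pre-drug requirement biases the comparison.* Whether a strictly pre-drug echo exists cannot depend on masked drug not yet started.
- *That aim 1 as a whole suffers.* Its OI/OSI and PaO2 part at 24 h is untouched.
- *That the cost of the rule is 57, 43 or 31%.* Those figures also include the separate gain from replacing a change score with baseline adjustment.

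The number of infants dropped is also not defined until the windows agree. The baseline echo is pre-drug in Section 3.2(iii). Section 4.1.2 says "prior to initiation of study drug or within 6 hours of initiation of study-drug is preferred as a baseline study", and the synopsis also uses 6 h. Section 5.4 uses 2 h. The follow-up is 24-72 h in Section 3.2(iii) and the echo closest to 24 h in Section 4.2.5; the synopsis places the second echo at 6-36 h. A baseline taken after drug start would weaken the no-bias argument: Section 2.3.3 reports that neonates given no loading dose reach half of steady state by 2 h.

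**What to change.** Amend Sections 3.2(iii) and 5.4 before unblinding:
- Analyse every infant with a 24-72 h echo.
- For tricuspid velocity and ejection fraction, use a longitudinal model with a common pre-drug mean, adjusted for HRF stratum. Modelling the follow-up value on arm, HRF stratum and pre-drug value with a missing indicator is an alternative. The longitudinal model is preferable if the correlation may be high.
- For septal position and shunt direction, model the follow-up category on arm, HRF stratum and pre-drug category with a missing indicator.
- Keep paired change as a sensitivity analysis.
- State one baseline window and one follow-up window, and use them throughout.
- Report by arm how many infants had each echo, with reasons for absence where known, and state that selection into a clinically triggered 24-72 h echo remains.

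The cost is SAP wording and one extra model per measure. No further echocardiograms are needed, since data from up to four clinical ones are already recorded. The small downside is that the headline estimate becomes an adjusted arm difference instead of a mean paired change.

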- (iii) Change in echocardiographic findings – velocity of tricuspid regurgitation, left ventricular ejection fraction, position of the interventricular septum and direction of shunt at the PDA and PFO level – prior to and 24-72h after starting the study medication. This outcome will be available only for those infants who have a pre-study drug echocardiogram and a second echocardiogram between 24-72 h after initiation of study drug. These data will be extracted from echocardiograms performed for clinical indications.
- (iv) Vasoactive Inotrope score and systemic blood pressure
- (v) Area under the curve for inspired oxygen after initiation of the study drug over the first 72 hours of study-drug infusion (or prior to ECMO or death, whichever is earlier) (Note: inspired oxygen and ventilator data from 4 time points per day – every 6 hours will be recorded to calculate area under the curve),
- (vi) If subsequent to the study drug, any additional inotrope or pulmonary vasodilator is used (such as iNO), we will evaluate the oxygenation response to these agents. If inotropes or vasodilators were used prior to the initiation of study drug, similar values will be recorded. The OI or OSI and $\text{PaO}_2/\text{FiO}_2$ ratio prior to and after initiation of the inotrope / vasodilator are recorded (these data are recorded at 6 hour intervals; the date and time of initiation of individual inotropes and vasodilators is recorded). The change in OI or OSI and $\text{PaO}_2/\text{FiO}_2$ ratio in response to these agents is evaluated as a continuous variable and arbitrarily classified into responders, partial responders and non-responders similar to prior trials (NINOs 1997, 1997).
 - a. complete response is defined as an increase in $\text{PaO}_2/\text{FiO}_2$ ratio $> 20 \text{ mmHg}$ from baseline,
 - b. partial response is an increase in $\text{PaO}_2/\text{FiO}_2$ ratio of 10 to 20 mmHg from baseline,
 - c. no response is defined as an increase of $< 10 \text{ mmHg}$ (or a decrease) in $\text{PaO}_2/\text{FiO}_2$ ratio from baseline,

- d. the site of sampling (preductal vs. postductal) is also recorded. (Gien and Kinsella 2016); right radial and ulnar arterial lines/sticks will be considered preductal; Left radial and ulnar arterial samples are usually preductal but can occasionally be postductal; umbilical arterial lines and posterior tibial lines (both sides) are always postductal.

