4.2. DETAILED STUDY PROCEDURES

For the purpose of the study, time period prior to study drug is defined as 12 hours prior to initiation to 30 minutes prior to initiation of study drug. Baseline is defined as the period 30 min prior to initiation of study drug. The monitoring period is defined as the period of study drug infusion and the first 24-hours following study drug cessation.

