- (ii) Diagnosed with severe or life-threatening renal dysfunction as defined in the MOP
- (iii) Diagnosed with severe or life-threatening arrhythmia as defined in the MOP not attributed to other causes such as electrolyte disturbances or a central line in the right atrium
- (iv) Diagnosed with severe or life-threatening intracranial bleed as defined in the MOP
- (v) Confirmed trisomy 13 or 18 by chromosomal analysis

Note: Respiratory deterioration is common in the natural history of CDH and should not be a reason for discontinuing study drug.

Duration of study intervention

In the absence of complications:

- (i) Milrinone/placebo is continued until oxygenation improves and two OIs obtained at least one hour apart are less than 7 (OSI < 3.5, if no arterial blood gas is available), then weaned according to the protocol below, or
- (ii) Milrinone/placebo is weaned and discontinued after a maximum of 3 days of therapy (72 hours from the initiation).

Surgery and ECMO:

- (i) Milrinone/placebo should preferably be continued if the patient requires ECMO irrespective of the mode of ECMO – VA vs. VV (Reason: although pharmacokinetics and volume of distribution are altered, milrinone may be beneficial with improved cardiac function especially during VV ECMO). (Note: ECMO use varies from center to center, but averages around 30%. This will mean that a fair number of the high risk patients are excluded unless they are enrolled soon after birth)
- (ii) It is recommended that the study drug be continued through surgery. If the surgical team prefers to discontinue the study drug, this indication should be recorded and study drug weaned as per protocol.

(iii) Note: if the clinical team decides to wean the baby off the study drug prior to ECMO or surgery, these reasons are documented as indications for discontinuing the study drug. It is not considered a protocol deviation or violation to wean the medication prior to surgery or ECMO. If serious, potentially drug-related complications occur, drug should be discontinued immediately (without weaning).

Study drug discontinuation criteria:

Milrinone/placebo is discontinued (without weaning) if the patient develops 'severe' or 'life-threatening' hypotension, intracranial or extracranial hemorrhage, renal dysfunction or arrhythmia that cannot be attributed to other causes.

Note:

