Criteria for re-initiation of study drug:

After the patient has met criteria for study drug discontinuation once (due to improvement in oxygenation and meeting OI criteria, or due to side effects such as severe hypotension, intracranial bleeding or renal dysfunction), study drug is discontinued and cannot be reinitiated even if the indication for initial discontinuation is resolved (for e.g., OI exceeds 10 after cessation of study drug or hypotension is resolved and blood pressure is normal etc.,). The clinical team may start open-label milrinone.

During the post-study drug infusion period, data regarding open-label milrinone use, pressor use, and vasodilator use will be recorded for 24 hours after cessation of study-drug.

Fluid intake:

- (i) As systemic hypotension and fluid bolus administration are common in patients with CDH and PPHN, it is important to record daily fluid intake.
- (ii) Total fluid intake (including maintenance fluids/TPN, flushes, medications, boluses and blood products) will be recorded for three 24-hour periods as entered in the nursing notes/EMR (please see MOP for details).

Clinical criteria for ECMO:

The decision to place an infant with CDH on ECMO is ***entirely up to the clinical team***. Many centers prefer to use ECMO for preoperative stabilization. The following general guidelines are provided as criteria for ECMO (Reiss, Schaible et al. 2010) (Snoek, Reiss et al. 2016):

- (i) Oxygenation index is consistently ≥ 40 for at least 3 h and/or
- (ii) Inability to maintain preductal saturations $> 85\%$ or postductal saturations $> 70\%$ and/or
- (iii) Increased PaCO_2 and respiratory acidosis with $\text{pH} < 7.15$ despite optimization of ventilator management and/or
- (iv) $\text{PIP} > 28 \text{ cm H}_2\text{O}$ or mean airway pressure $> 17 \text{ cm H}_2\text{O}$ is required to achieve saturations $> 85\%$ and $\text{PaCO}_2 < 65 \text{ mmHg}$ and/or
- (v) Inadequate oxygen delivery with metabolic acidosis as measured by elevated lactate $\geq 5 \text{ mM/L}$ and $\text{pH} < 7.15$ and/or
- (vi) Systemic hypotension (mean blood pressure $< 30 \text{ mmHg}$), resistant to fluid and inotropic support, resulting in hypoperfusion and/or oliguria (urine output $< 0.5 \text{ mL/kg/h}$) for at least 12-24h

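### The inspired-oxygen AUC is cut at ECMO or death without time-averaging, so early failure lowers the score; the Cox plot is limited to an undefined group of responders

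*Combined protocol and SAP*

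**What the plan says.** The protocol summary defines secondary outcome (v) as "Area under the curve for inspired oxygen after initiation of the study drug over the first 72 hours of study-drug infusion". Section 3.2, outcome (v), has the same item with its cut-off: "over the first 72 hours of study-drug infusion (or prior to ECMO or death, whichever is earlier". Values are recorded every 6 hours. Section 5.4 gives this outcome no rule of its own. Continuous outcomes other than the primary are to be handled like the primary, by a general linear model adjusted for HRF severity.

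Three other passages bear on the observation window:

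- Section 4.2.5 lets the infusion end before 72 h: "Milrinone/placebo is continued until oxygenation improves and two OIs obtained at least one hour apart are less than 7".
- Section 4.2: "The monitoring period is defined as the period of study drug infusion and the first 24-hours following study drug cessation".
- Section 4.2.5, on the period after infusion: "data regarding open-label milrinone use, pressor use, and vasodilator use will be recorded for 24 hours after cessation of study-drug". Inspired oxygen is not in that list.

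On survival, Section 5.4 says Cox models "will be used to plot proportion of responders who survive without ECMO against survival time in hours". The same section says "All analysis will be by intention-to-treat". The only responder classes in the plan are in Section 3.2, outcome (vi). They are changes in PaO2/FiO2 after other inotropes or vasodilators started after study drug. Agents started earlier may also be covered: "If inotropes or vasodilators were used prior to the initiation of study drug, similar values will be recorded".

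**The concern.** An area under a curve accumulates with time. If observation stops at ECMO or death and the area is not divided by the hours observed, the infants who do worst have the fewest hours to add up. Truncation therefore pushes the comparison in favour of whichever arm has more early failures. The plan deals with this elsewhere: outcome (i) assigns at least OI 40 or OSI 20 on ECMO or death before 24 h, and the primary outcome and outcome (ii) carry a last value, which does not shrink when follow-up stops. Only outcome (v) lets early failure reduce the score.

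The wording of the window adds a second doubt. It could be read as ending when the infusion ends, which would also cut infants whose infusion stops for improvement.

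The Cox sentence is a separate matter. Responder status in outcome (vi) depends on having received another agent and is not a response to study drug. Restricting the plot to such infants selects a non-randomised subset, and the bias could go either way. This is the only time-to-event analysis described, and ECMO-free survival is the intended primary outcome of the definitive trial.

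**Working it through.** The plan gives no figure for the FiO2 area or the Cox plot, so there is none to reproduce.

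**Inputs from the documents.** Window 72 h, cut at ECMO or death, 6-hourly records (Section 3.2 (v)); 33 infants per arm (Section 5.1). The risk of ECMO or death is put at about 40%, but to discharge or day 120 (Section 5.1), not to 72 h.

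**Assumptions.** FiO2 levels, failure times and failure shares by 72 h are not in the documents and are assumed below. FiO2 is held constant within each infant, and non-failures have the same FiO2 distribution in both arms.

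**One infant against another.** Area = FiO2 × hours observed.

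- Failure at 24 h on FiO2 1.0: 1.0 × 24 = 24.0.
- No failure, FiO2 0.40 for 72 h: 0.40 × 72 = 28.8.
- An infant on FiO2 g who fails scores better than a non-failure on FiO2 f if failure comes before 72 × f / g hours. With g = 1.0 this is 28.8 h at f = 0.40 and 36 h at f = 0.50. With g = 0.9 it is 32 h and 40 h.
- Divided by hours observed, the failing infant scores 1.00 against 0.40, which is the right order.

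**Arm against arm.** Expected difference (higher-failure arm minus the other) = difference in failure share × (mean failure area − mean non-failure area). Failures are uniform on FiO2 0.8–1.0 (mean 0.9) and failure times are uniform, so the mean time is 26 h for 4–48 h and 38 h for 4–72 h. Non-failures on 0.3–0.7 average 0.50 × 72 = 36.0; on 0.21–0.6 they average 0.405 × 72 = 29.2.

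| Failure shares | Failure times | Non-failure FiO2 | Expected area difference | Expected mean-FiO2 difference |
|---|---|---|---|---|
| 40% v 20% | 4–48 h | 0.3–0.7 | 0.20 × (0.9 × 26 − 36.0) = −2.52 | 0.20 × (0.9 − 0.5) = +0.08 |
| 40% v 20% | 4–72 h | 0.3–0.7 | 0.20 × (0.9 × 38 − 36.0) = −0.36 | +0.08 |
| 40% v 20% | 4–72 h | 0.21–0.6 | 0.20 × (0.9 × 38 − 29.2) = +1.0 | 0.20 × (0.9 − 0.405) = +0.10 |
| 25% v 20% | 4–48 h | 0.3–0.7 | 0.05 × (23.4 − 36.0) = −0.63 | 0.05 × 0.4 = +0.02 |

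A negative area difference favours the arm with more failures.

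**Simulation.** With 6,000 trials of 33 per arm, the mean area differences in the same order were −2.53, −0.34, +0.99 and −0.60. The between-trial SD in the three 40% v 20% rows was 2.7–3.0. Trials with p < 0.05 in the wrong direction made up 15%, 3% and 1% of the first three rows and about 4% of the last. Chance alone gives about 2.5%. With 30% failing in both arms the mean difference was 0.04, so there is no bias when failure is balanced.

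**Responders.** No arithmetic applies. Section 5.4 names responders as the group to be plotted; Section 3.2 (vi) defines the class by response to agents other than study drug; Section 5.4 also requires every analysis to be by intention-to-treat. Read literally, the first and third cannot both be met.

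**The case against.** The strongest objection is that the net direction is not fixed. One scenario above has the correct sign, another is near zero, and two of the four wrong-direction rates (3% and 1%) are at or below the chance level. The 15% needs a two-fold imbalance in failure with every failure before 48 h; changing only the non-failure FiO2 to 0.21–0.6 reduces it to −1.2 FiO2-hours and 7%. This stands as a limit on size. It does not remove the defect, because truncation always pulls a failing infant's area down, and a lower area cannot be interpreted without knowing who failed and when.

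The correct sign of mean FiO2 follows partly from assuming higher FiO2 in failures, and a mean over the hours before failure is itself still cut by failure. That is fair, and it is why a sensitivity analysis is needed alongside.

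The window can reasonably be read as 72 h from initiation, since only ECMO and death are named as early ends. That is probably the intent, and one sentence would settle it. On the other reading, infants who improve would have shortened areas, which is a different distortion.

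Finally, outcome (v) is one of ten secondary outcomes, outcomes (i) and (viii) would be reported beside it, and the responder wording may simply be loose. A restricted plot could also still be split by arm. These points limit the weight of the concern, but the text remains as it is.

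**Conclusion.** Both parts hold. As written, outcome (v) always lowers the area of an infant who reaches ECMO or death before 72 h and shifts the comparison toward the arm with more early failures. Whether that reverses the arm-level result depends on failure times and FiO2 levels that the documents do not give. Under the assumptions shown, the difference at 40% v 20% failure ranges from −2.5 to +1.0 FiO2-hours, and wrong-direction significance from 15% to 1%. Time-weighted mean FiO2 keeps the correct sign throughout (+0.02 to +0.10).

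The Cox plot, read literally, covers a non-randomised subset and conflicts with the plan's own intention-to-treat statement. This part matters less, because outcome (viii) still reports ECMO-free survival for all infants. The plan should be corrected on both counts. Confidence in the size of the AUC effect is medium.

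**What to change.** **Outcome (v), in the protocol summary and Section 3.2.**

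- Analyse time-weighted mean FiO2: area divided by hours observed, from study-drug start to the earliest of 72 h, ECMO or death.
- Use baseline FiO2 as the time-0 value, so that infants who fail before the first 6-hourly record still have a score.
- Add a sensitivity analysis giving infants with ECMO or death a prespecified worst value or rank up to 72 h.
- State that the window runs from study-drug start and does not close when the infusion stops early, and confirm that 6-hourly FiO2 is recorded to 72 h in those infants.

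**Section 5.4.** Remove the restriction to responders. Fit the Cox model and curves to all randomised infants by arm, adjusted for HRF severity. Label any responder plot descriptive.

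**Cost.** Mostly wording, with possibly some extra chart extraction. For an infant whose infusion stops at 24 h, the monitoring period ends at 48 h, so the values at 54, 60, 66 and 72 h would be added. If the post-infusion list in Section 4.2.5 is exhaustive, those from 30 to 48 h would be needed too. Outcome (ii) already needs FiO2 at 72 h to compute OI.

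**Downsides.** Mean FiO2 alone gives no extra penalty for ECMO or death, and the assigned worst value is a convention, so both results should be reported.
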